#### 9.1.5 Severity of PTEs and AEs

The different categories of intensity (severity) are characterized as follows:

Mild: The event is transient and easily tolerated by the subject.

Moderate: The event causes the subject discomfort and interrupts the subject's usual activities.

Severe: The event causes considerable interference with the subject's usual activities.

#### 9.1.6 Causality of AEs

The relationship of each AE to study immunotherapy will be assessed using the following categories:

Related: An AE that follows a reasonable temporal sequence from administration of the immunotherapy (including the course after withdrawal of the study immunotherapy), or for which possible involvement of the immunotherapy cannot be ruled out, although factors other than the immunotherapy, such as underlying diseases, complications, concomitant drugs and concurrent treatments, may also be responsible.

**Not Related:** An AE that does not follow a reasonable temporal sequence from administration of the immunotherapy and/or that can reasonably be explained by other factors, such as underlying diseases, complications, concomitant drugs and concurrent treatments.

#### 9.1.7 Relationship to Study Procedures

Relationship (causality) to study procedures should be determined for all PTEs and AEs.

The relationship should be assessed as Related if the investigator considers that there is reasonable possibility that an event is due to a study procedure. Otherwise, the relationship should be assessed as Not Related.

#### 9.1.8 Start Date

The start date of the AE/PTE is the date that the first signs/symptoms were noted by the subject and/or physician.

#### 9.1.9 Stop Date

The stop date of the AE/PTE is the date at which the subject recovered, the event resolved but with sequelae or the subject died.

#### 9.1.10 Frequency

Episodic AEs/PTE (eg, vomiting) or those which occur repeatedly over a period of consecutive days are intermittent. All other events are continuous.

#### 9.1.11 Action Concerning Study Medication

- Stop immunotherapy – the study immunotherapy is stopped due to the particular AE.
- Immunotherapy not changed – the particular AE did not require stopping the study immunotherapy.
- Unknown – only to be used if it has not been possible to determine what action has been taken.
- Not Applicable – the immunotherapy was stopped for a reason other than the particular AE eg, the study has been terminated, the subject died, dosing with the study immunotherapy was already stopped before the onset of the AE.

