### **6.4 Criteria for Discontinuation or Withdrawal of a Subject**

The primary reason for discontinuation or withdrawal of the subject from the study or study medication should be recorded in the CRF using the following categories. For screen failure subjects, refer to Section 8.1.11.

1. Pretreatment event (PTE) or adverse event (AE). The subject has experienced a PTE or AE that requires early termination because continued participation imposes an unacceptable risk to the subject's health or the subject is unwilling to continue because of the PTE or AE.
2. Significant protocol deviation. The discovery postrandomization or after the first dose of study immunotherapy that the subject failed to meet protocol entry criteria or did not adhere to protocol requirements, and continued participation poses an unacceptable risk to the subject's health.
3. Lost to follow-up. The subject did not return to the clinic and attempts to contact the subject were unsuccessful. Attempts to contact the subject must be documented.
4. Voluntary withdrawal. The subject (or subject's legally acceptable representative) wishes to withdraw from the study. The reason for withdrawal, if provided, should be recorded in the

CRF. All attempts should be made to determine the underlying reason for the withdrawal and, where possible, the primary underlying reason should be recorded.

5. Study termination. The sponsor, IRB, or regulatory agency terminates the study.
6. Pregnancy. The subject is found to be pregnant.

Note: If the subject is found to be pregnant, the subject must be withdrawn immediately. The procedure is described in Section 8.1.10.

7. The investigator has determined that continued participation would pose an unacceptable risk to the subject.

Note: After the 30 minute wait period, subjects that develop local swelling at the site of the injection greater than 50mm diameter will have their next dose decreased by one step. Subjects having a Grade 1-2 systemic reaction will have their next injection decreased by two steps. Systemic reaction Grade 3 or more will require withdrawal from the study. Systemic reactions are defined by the World Allergy Organization anaphylaxis grading system (13).

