#### **9.1.3 Additional Points to Consider for PTEs and AEs**

An untoward finding generally may:

- Indicate a new diagnosis or unexpected worsening of a pre-existing condition. (Intermittent events for pre existing conditions underlying disease should not be considered PTEs or AEs.)
- Necessitate therapeutic intervention.
- Require an invasive diagnostic procedure.
- Require discontinuation or a change in dose of study medication or a concomitant medication.
- Be considered unfavorable by the investigator for any reason.
- PTEs/AEs caused by a study procedure (eg, a bruise after blood draw) should be recorded as a PTE/AE.

Diagnoses vs signs and symptoms:

- Each event should be recorded to represent a single diagnosis. Accompanying signs or symptoms should NOT be recorded as additional AEs. If a diagnosis is unknown, sign(s) or symptom(s) should be recorded appropriately as a PTE(s) or as an AE(s).

Pre-existing conditions:

- Pre-existing conditions (present at the time of signing of informed consent) are considered concurrent medical conditions and should NOT be recorded as PTEs or AEs. Baseline evaluations (eg, laboratory tests, ECG, X-rays etc.) should NOT be recorded as PTEs unless

related to study procedures. However, if the subject experiences a worsening or complication of such a concurrent condition, the worsening or complication should be recorded appropriately as a PTE (worsening or complication occurs before start of study medication) or an AE (worsening or complication occurs after start of study medication). Investigators should ensure that the event term recorded captures the change in the condition (eg, “worsening of...”).

- If a subject has a pre-existing episodic condition (eg, gout, epilepsy) any occurrence of an episode should only be captured as a PTE/AE if the episodes become more frequent, serious or severe in nature, that is, investigators should ensure that the AE term recorded captures the change in the condition from Baseline (eg “worsening of...”).

Worsening of PTEs or AEs:

- If the subject experiences a worsening or complication of a PTE after starting administration of the study medication, the worsening or complication should be recorded appropriately as an AE. Investigators should ensure that the AE term recorded captures the change in the condition (eg, “worsening of...”).

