#### ***9.2.1.2 PTE and AE Reporting***

At each study visit, the investigator will assess whether any subjective AEs have occurred. A neutral question, such as “How have you been feeling since your last visit?” may be asked. Subjects may report AEs occurring at any other time during the study. Subjects experiencing a serious PTE must be monitored until the symptoms subside and any clinically relevant changes in laboratory values have returned to baseline or there is a satisfactory explanation for the change. Non-serious PTEs, related or unrelated to the study, need not to be followed-up for the purposes of the protocol.

All subjects experiencing AEs, whether considered associated with the use of the study immunotherapy or not, must be monitored until the symptoms subside and any clinically relevant changes in laboratory values have returned to baseline or until there is a satisfactory explanation

for the changes observed. All PTEs and AEs will be documented in the PTE/AE page of the CRF, whether or not the investigator concludes that the event is related to the immunotherapy. The following information will be documented for each event:

1. Event term.
2. Start and stop date.
3. Severity.
4. Investigator's opinion of the causal relationship between the event and administration of study immunotherapy (related or not related) (not completed for PTEs).
5. Investigator's opinion of the causal relationship to the study immunotherapy, including the details of the suspected immunotherapy administration.
6. Action concerning study immunotherapy (not applicable for PTEs).
7. Outcome of event.
8. Seriousness.

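### The AE action list has no dose-reduced category, so every reaction managed by a Section 6.4 dose reduction is coded as immunotherapy not changed

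*Combined protocol and SAP*

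**What the plan says.** The note at the end of protocol Section 6.4 sets three responses to a reaction after an injection:

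- Large local reaction: "subjects that develop local swelling at the site of the injection greater than 50mm diameter will have their next dose decreased by one step".
- Mild systemic reaction: "Subjects having a Grade 1-2 systemic reaction will have their next injection decreased by two steps".
- More severe systemic reaction: "Systemic reaction Grade 3 or more will require withdrawal from the study".

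Section 9.2.1.2 lists eight items to be documented for each event, and item 6 is the action concerning study immunotherapy. Section 9.1.11 gives the four permitted answers. The first is "Stop immunotherapy – the study immunotherapy is stopped due to the particular AE". The second is "Immunotherapy not changed – the particular AE did not require stopping the study immunotherapy". The third, Unknown, is reserved for cases where the action could not be determined. The fourth, Not Applicable, covers immunotherapy stopped for a reason other than the AE in question.

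Section 9.1.3, on what may count as an untoward finding, includes this item: "Require discontinuation or a change in dose of study medication or a concomitant medication". A change in dose is named there alongside discontinuation, as a separate consequence.

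Section 12.1.4 tabulates treatment-emergent AEs overall, by system organ class and by preferred term. The SAP compares AE rates between arms. Neither mentions the action taken or dose reductions.

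**The concern.** The protocol prescribes three responses to a reaction: lower by one step, lower by two steps, or withdraw. The field meant to record the response can express only the last. A site that follows both sections exactly lowers the dose because of an AE and then records for that AE that immunotherapy was not changed.

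The field matters because this is a 16-injection escalation with safety as a secondary endpoint (protocol 2.1.2 and 4.1.2; SAP, Secondary Endpoint). Section 7.1.4 predicts very few adverse events because the allergen doses are low. Reactions that oblige the site to step back bear directly on that prediction. The placebo contains histamine intended to mimic local reactions, so reductions could occur in either arm and are informative only when counted by arm. As written, a listing of AEs by action taken would show stops, and every other known action during ongoing treatment would appear as no change.

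**Working it through.** The plan states no figure on this point, so there is none to reproduce. The check maps each rule in 6.4 to the categories in 9.1.11.

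| Rule in 6.4 | Required response | Fits Stop? | Fits Unknown? | Fits Not Applicable? | Resulting code |
|---|---|---|---|---|---|
| Local swelling over 50 mm | Next dose down one step | No, treatment continues | No, the action is known | No, not stopped for another reason | Not changed |
| Systemic reaction, Grade 1-2 | Next dose down two steps | No | No | No | Not changed |
| Systemic reaction, Grade 3 or more | Withdrawal | Yes | – | – | Stop |

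Both dose-reduction rules, and so two of the three reaction rules, end in the not-changed category.

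**Could another AE field recover the information?** The other items in 9.2.1.2 are event term, dates, severity, causality (items 4 and 5), outcome and seriousness. Severity under 9.1.5 is mild, moderate or severe, defined by tolerability and interference with activities. It is not the World Allergy Organization grade on which 6.4 acts. No item asks for that grade or for the swelling diameter. An event term or the item 5 detail might happen to mention a reduction, but neither is a structured field for it.

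**How large a dose change does the code cover?** The inputs are the volume per mix and the nominal dilution in Appendix H. The protocol does not define a step, so one step is assumed to be one row of that schedule. Relative allergen dose = volume per mix ÷ dilution factor:

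- Vial #5: 0.05/625 = 0.00008; 0.10/625 = 0.00016; 0.15/625 = 0.00024; 0.20/625 = 0.00032.
- Vial #4, first two rows: 0.05/125 = 0.0004; 0.10/125 = 0.0008.

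The pattern repeats in each vial. Proportional reduction = 1 − (lower dose ÷ reference dose):

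- One step: 1 − 0.00008/0.00016 = 50%; 1 − 0.00016/0.00024 = 33%; 1 − 0.00024/0.00032 = 25%; 1 − 0.00032/0.0004 = 20%.
- Two steps: 1 − 0.00008/0.00024 = 67%; 1 − 0.00016/0.00032 = 50%; 1 − 0.00024/0.0004 = 40%; 1 − 0.00032/0.0008 = 60%.

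One step down is therefore a 20% to 50% lower allergen dose, and two steps a 40% to 67% lower dose, relative to the row from which the steps are counted. Here that row is taken to be the dose just given.

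**The case against.** The strongest reply is that this is a coarse code list with little practical effect. Much of that reply stands.

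- **Literal truth.** By its own definition the not-changed category means only that stopping was not required, so a site using it after a reduction is following the definition. This is correct, and it shows that the fault lies in the list and not with the site. The label still says something that 6.4 contradicts.
- **The reactions are not lost.** A reader might infer that the AE data would show none of these events. The documents do not support that. All AEs are documented whatever the action taken, 12.1.4 tabulates them by system organ class and preferred term, and the SAP compares AE rates. Only the link from reaction to reduction is missing.
- **Reconstruction is possible.** A reader might infer that the reductions cannot be found at all. However, item 5 of 9.2.1.2 asks for details of the suspected administration, Appendix J puts vial number, dose and reactions on one sheet per visit, and Appendix H fixes the planned dose. With about 36 subjects at one site, manual linkage is feasible. No section plans it.
- **No planned result changes.** Neither 12.1.4 nor the SAP tabulates by action taken. The comparison of subjects stopping treatment, in the study summary, depends on stops, which the list can code.
- **Unseen forms.** The AE CRF page is not in the documents, and data-handling details are left to a Data Management Plan (Section 11.0). An extra option on the form cannot be excluded, but 9.1.11 would still need correcting.

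**Conclusion.** The point holds, with modest consequence. Sections 6.4, 9.1.3 and 9.1.11 are inconsistent: every reaction managed by dose reduction under 6.4 is coded as no change in a required AE field, no structured AE field in the protocol identifies the reduction, and no planned analysis counts it.

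Two stronger readings are tempting. The first is that every dose-limiting reaction is miscoded; that fails because Grade 3 or more leads to withdrawal and is correctly coded as a stop. The second is that a planned safety result would be wrong; none uses the field. What the trial loses is the ability to report reaction-driven reductions by arm without rebuilding them from visit sheets.

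The number of subjects affected cannot be estimated. With 36/2 = 18 per arm it could be anywhere from 0 to 18, and the documents give no rate for swelling over 50 mm or for Grade 1-2 reactions. The rate of under 20% in 9.1.4 concerns mild local reactions generally and should not be substituted. The 20-50% and 40-67% dose changes rest on nominal dilutions and on one step being one row of Appendix H.

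**What to change.** Reconcile 9.1.11 with 6.4 and 9.1.3:

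1. Add a dose-reduced category to 9.1.11 and to the AE CRF page.
2. Redefine the not-changed category as no change to the dose because of the AE.
3. In 12.1.4 and the SAP, add a descriptive count, by arm, of subjects with at least one reaction-driven dose reduction. No test is needed.

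Optionally, record on the AE page the systemic grade or swelling diameter that triggered the reduction. Both must already be assessed to apply 6.4.

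The cost is one tick-box and one table row, with no new procedure. No change to the dose-reduction rule is proposed.

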#### 9.1.12 Outcome

- Recovered/Resolved – Subject returned to first assessment status with respect to the AE/PTE.
- Recovering/Resolving – the intensity is lowered by one or more stages: the diagnosis or signs/symptoms has almost disappeared; the abnormal laboratory value improved, but has not

returned to the normal range or to baseline; the subject died from a cause other than the particular AE/PTE with the condition remaining “recovering/resolving”.

- Not recovered/not resolved – there is no change in the diagnosis, signs or symptoms; the intensity of the diagnosis, signs/ symptoms or laboratory value on the last day of the observed study period has got worse than when it started; is an irreversible congenital anomaly; the subject died from another cause with the particular AE/PTE state remaining “Not recovered/not resolved”.
- Resolved with sequelae – the subject recovered from an acute AE/PTE but was left with permanent/significant impairment (eg, recovered from a cardiovascular accident but with some persisting paresis).
- Fatal – the AEs/PTEs which are considered as the cause of death.
- Unknown – the course of the AE/PTE cannot be followed up due to hospital change or residence change at the end of the subject’s participation in the study.

## **9.2 Procedures**

### **9.2.1 Collection and Reporting of AEs**

#### ***9.2.1.1 PTE and AE Collection Period***

Collection of PTEs will commence from the time the subject signs the informed consent to participate in the study and continue until the subject is first administered study immunotherapy (visit 2) or until screen failure. For subjects who discontinue prior to study immunotherapy administration, PTEs are collected until the subject discontinues study participation.

Collection of AEs will commence from the time that the subject is first administered study immunotherapy (visit 2). Routine collection of AEs will continue until visit 14 .

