### **8.3 Schedule of Observations and Procedures**

The schedule for all study-related procedures for all evaluations is shown in Appendix A. Assessments should be completed at the designated visit/time point(s).

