### 8.3.4 Final Visit or Early Termination

The Final Visit will be performed on visit 18 or at an Early Termination Visit. The following procedures will be performed and documented:

- Physical examination.
- Vital signs.
- Concomitant medications.
- Concurrent medical conditions.
- Efficacy assessment.
- Safety assessment.
- Blood draw.

For all subjects receiving study medication, the investigator must complete the End of Study CRF page.

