### 8.3.5 Follow-up

Follow-up will begin the first day after the last injection and will continue until for 30 days at which time a final in-clinic visit (visit 18) will be conducted for a safety assessment and blood draw.

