#### **12.1.4 Safety Analysis**

Overall safety and tolerability will be assessed by evaluating the incidence of TEAE, laboratory tests, vital signs, and other safety variables. Treatment-emergent adverse events will be defined as any AEs, regardless of relationship to study immunotherapy, that occur on or after the first double blind immunotherapy administration date and up to 30 days after the last dose date of the double-blind immunotherapy and will be assigned to the treatment at the time of the event.

Treatment-emergent adverse events will be summarized using the full analysis set. Adverse events will be summarized using the MedDRA coding dictionary. In general, AEs will be tabulated at each of the following levels: overall summary (subject with at least 1 AE), the MedDRA system organ class (SOC) and the MedDRA preferred term (PT). Tabulations at each level of a term will present count (n) and percentage of subjects reporting any event for that term. Subjects reporting more than one occurrence for the term (level) being summarized will be counted only once and assigned to the drug assignment at time of the event.

Laboratory test variables will be summarized by active PMA or placebo assignment and study visit using descriptive statistics. Laboratory data collected from baseline and up to 7 days after a subject's last dose of study immunotherapy will be included in the analysis. Markedly abnormal laboratory values will be determined and listed by study group. The number and percentage of subjects with marked abnormality in each of the laboratory parameters will be presented.

Descriptive statistics will be used to summarize vital signs by treatment group and study visit. Vital sign data collected from baseline and up to a subject's last dose of study immunotherapy will be included in the analysis.

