## **Appendix A Schedule of Study Procedures**

Study Week:	Screen (Week 1)	Washout (Week 1-2)	Treatment (Week 3-11)	Follow-up safety assessment (Week 14)
Visit Number:	1	N/A	2-17	18
Discussion and Recruitment	X			
Informed consent	X			
Inclusion/exclusion criteria	X			
Demographics and medical history	X			
Medication history	X			
Physical examination	X			
Vital signs	X		X	
Weight and height	X			
Concomitant medications	X	X	X	X
Concurrent medical conditions	X			X
Skin Testing	X			
Blood Draw	X			X
Post-immunotherapy safety f/u				X
Administer immunotherapy/safety f/u			X	
Clinical Survey (RQLQ) and TNSS	X		X	X
Site return compliance	X		X	X
PTE assessment	X	X		
AE assessment		X	X	X

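### Section 9.2.1.1 stops routine AE collection at visit 14, the 13th of 16 injections, against the rest of the protocol, and the SAE procedure in 9.2.2 takes its period from that sentence

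*Combined protocol and SAP*

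**What the plan says.** Section 9.2.1.1 starts AE collection at the first injection, which it calls visit 2, and then sets the end: "Routine collection of AEs will continue until visit 14".

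Other parts of the protocol go further:

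- Section 9.2.1.2: "At each study visit, the investigator will assess whether any subjective AEs have occurred".
- Appendix A marks AE assessment in the treatment column (visits 2 to 17) and again at follow-up (visit 18, week 14). Section 8.3 tells staff to carry out assessments as scheduled there.
- Section 8.3.4: "The Final Visit will be performed on visit 18 or at an Early Termination Visit". A safety assessment is among its listed procedures.
- Section 8.3.5 runs follow-up for 30 days from the last injection, when "a final in-clinic visit (visit 18) will be conducted for a safety assessment and blood draw".
- Section 12.1.4 counts treatment-emergent AEs "up to 30 days after the last dose date of the double-blind immunotherapy". The Study Summary gives the same window.

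Section 9.2.2 requires its SAE procedure for events within the AE collection period. After that period it asks only for SAEs that are volunteered to the investigator and judged related to taking part in the study.

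**The concern.** The section that is titled as the collection period gives an end point that every other relevant passage contradicts. A coordinator who follows 9.2.1.1 would stop routine AE collection while the dose is still being raised. The treatment-emergent AE tables would then not cover the window that 12.1.4 says they cover. The AE profile is a secondary endpoint in protocol section 2.1.2 and in the SAP, and the SAP compares AE rates between groups.

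The sharper consequence is in 9.2.2. No other section defines the AE collection period, so a wrong end point in 9.2.1.1 also shortens the period in which every SAE must go through the 9.2.2 procedure. An SAE considered unrelated, arising between visit 14 and the end of follow-up, would not meet the narrower condition that applies afterwards.

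**Working it through.** The plan states no figure to reproduce. The check is a count of visits, then dose and time shares that describe the literal reading of 9.2.1.1 only.

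**Position of visit 14.** Appendix H lists 16 injections at visits 2 to 17, which agrees with Appendix A and with the numbering in 9.2.1.1. Injection number = visit number − 1, so visit 14 is injection 13. Visits 15, 16 and 17 are injections 14 to 16, and visit 18 is the follow-up.

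**Share of scheduled active dose after visit 14.** The inputs are the per-mix volumes in Appendix H (0.05, 0.10, 0.15 and 0.20 ml at each dilution, 0.50 ml in total) and the nominal dilutions 1:625, 1:125, 1:25 and 1:5. Dose is volume divided by dilution factor, in ml of vial #1 per mix.

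- Total: 0.50/625 + 0.50/125 + 0.50/25 + 0.50/5 = 0.0008 + 0.0040 + 0.0200 + 0.1000 = 0.1248.
- Visits 15 to 17: (0.10 + 0.15 + 0.20)/5 = 0.0900.
- Share: 0.0900/0.1248 = 72.1%.

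These are the three largest doses: 0.02, 0.03 and 0.04, against 0.01 at visit 14.

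The preparation volumes in section 7.1.1 give slightly different factors: vial #2 is 105/20 = 5.25, #3 is 89/4 = 22.25, #4 is 5.25 × 22.25 = 116.8, and #5 is 22.25 × 22.25 = 495.1. The total becomes 0.1230, visits 15 to 17 give 0.45/5.25 = 0.0857, and the share is 69.7%.

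**Share of the 30-day window after visit 14.** Assume twice-weekly visits (section 5.1), with time counted from the first dose.

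- Visit 14 is 12 intervals on: 6 weeks, day 42.
- Visit 17 is 15 intervals on: 15 × 3.5 = day 52.5 at even spacing. With gaps of 2 and 5 days in either order it is day 49 + 2 = 51 or 49 + 5 = 54.
- The window closes 30 days later: day 82.5 (81 to 84).
- Share after visit 14: (82.5 − 42)/82.5 = 40.5/82.5 = 49.1%. The range is 39/81 = 48.1% to 42/84 = 50.0%.

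**What still applies to an unrelated SAE after visit 14.**

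| Section | Does it still apply? |
|---|---|
| 9.2.2, SAE procedure | No, if 9.2.1.1 is read literally |
| 9.2.1.2, AE enquiry at visits; CRF record of all AEs, with seriousness | Yes |
| 9.3.1, SUSARs and other applicable SAEs to the IRB | Yes, no visit cut-off |
| Appendix B item 12, notice to the sponsor within 24 hours | Yes, no end date |

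The documents therefore set two different SAE duties for the same days. They do not leave those days without any duty.

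**The case against.** The best defence is that visit 14 is an obvious slip and that staff will work from Appendix A. Two origins are plausible. It may stand for week 14, which Appendix A assigns to visit 18. Or it may survive from a shorter design: section 5.1 and the SAP's Study Design text still mention six weeks of treatment, and section 8.3.3 still lists visits 1 through 12. Twelve twice-weekly injections from visit 2 would end at visit 13, making visit 14 the follow-up. Both are inferences, and the documents do not settle which is right. The sentence uses visit numbers throughout, so it cannot simply be read as weeks. Either origin supports correcting it.

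The second defence is that little would be lost, and much of this stands. Sections 9.2.1.2 and 9.3.1, Appendix A and Appendix B item 12 keep AE enquiry, recording and SAE notice in force. What they do not repair is the period on which 9.2.2 depends.

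A reader might also infer that changing visit 14 to week 14 would leave a sizeable shortfall, because Appendix A runs treatment to week 11 (study days 71 to 77) and week 14 begins on day 92, only 15 days after day 77. The documents do not support that. Section 8.3.5 sets visit 18 at 30 days after the last injection, and section 1.2 calls the 14-week duration approximate. A first dose on day 15 puts the last dose on days 66 to 69, and 30 days later is days 96 to 99, at or one day past the end of week 14 (day 98). Even a day-21 start with the most uneven spacing ends on day 21 + 54 = 75, so day 77 is not reached. At most, the week labels should be reconciled with section 8.3.5.

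**Conclusion.** The contradiction is real and should be fixed. Section 9.2.1.1 ends routine AE collection at injection 13 of 16, against sections 9.2.1.2, 8.3.4, 8.3.5 and 12.1.4 and Appendix A, and 9.2.2 inherits the error.

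Its size depends on which passage staff follow. Under Appendix A and 9.2.1.2, AE enquiry continues to visit 18 and the defect is one of wording and of the 9.2.2 period. Under 9.2.1.1 taken literally, routine collection misses three injections carrying 72.1% of the nominal cumulative active dose (69.7% on the preparation volumes) and about 49% of the treatment-emergent window. The time share assumes twice-weekly visits; the injection count and dose shares do not. These are shares of exposure and time, not estimates of missed events.

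Two stronger conclusions might be drawn and are not supported. The first is that safety data after visit 14 will be lost or SAEs will go unreported: other sections still require capture and notice, so this is a risk and not a certainty. The second is bias between arms: the same rule applies to both groups, and nothing in the documents shows that it would act differently in them.

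**What to change.** In section 9.2.1.1, replace the visit 14 end point with: *until 30 days after the last dose of study immunotherapy, or until the visit 18 follow-up if that is later*. In section 9.2.2, add that the SAE reporting period is the same. Leave Appendix B item 12 as it is, since its notice requirement has no end date. When the remaining six-week and visits 1 through 12 text is reconciled with the eight-week schedule, align the Appendix A week labels with the 30-day timing in section 8.3.5.

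The cost is two sentences. Subjects who terminate early, or whose visit 18 falls before day 30, may need one further contact. Section 1.2 already allows the one-month follow-up by telephone, although section 8.3.5 describes an in-clinic visit. The change uses the protocol's own window and alters no dose or treatment rule.
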